- AEs, laboratory parameters, and vital signs will be reported descriptively, based on the safety population (all randomized patients who received at least one dose or partial dose of study treatment). Safety will also be assessed by a review of all safety endpoints including adverse events (AEs), laboratory examinations, and electrocardiogram test.

Unless otherwise specified, all statistical assessments will be two-sided under significant level of 0.05.

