
1.2. Study Rationale

Statins-cholesterol lowering drugs are the first-choice treatments for the primary and secondary prevention of CVD, if the patient still has elevated TG and/or low HDL-C despite intensive lifestyle intervention, and addressing compliance with pharmacotherapy and secondary causes of dyslipidemia, additional lipid-modifying therapy may be considered. Along with the long-term treatment with statins in combination with other hypolipidemic drugs or alone, the safety has drawn a particular attention in clinic, such as the elevation of transaminase and rhabdomyolysis, which have raised an idea of developing the other types of lipid-lowering agents from botanic materials.

The primary hypothesis is that Antroquinonol treatment will be well tolerated and will result in greater lowering of TG at week 12 than placebo in patients with hypercholesterolemia and hyperlipidemia. The primary goal is to determine if Antroquinonol will provide greater TG lowering effect than placebo.

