2.2. Secondary objectives

Secondary objectives are:

- (1) To evaluate the effects of 12 weeks of oral administration Antroquinonol compared with placebo on percentage change from baseline in other lipid parameters as lipid-lowering therapy.
- (2) To evaluate the effects of Antroquinonol on left ventricular diastolic function and arterial stiffness.
- (3) To evaluate the effect of Antroquinonol on fatty liver via computed tomography (CT) scanning.
- (4) To evaluate the safety and tolerability of 12 weeks of oral administration of Antroquinonol compared with placebo in subjects with hypercholesterolemia and hyperlipidemia

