6.2. Study Procedures

6.2.1. Screening (Day -14)

All patients must provide written informed consent before any study specific assessments or procedures are performed. A subject enrollment form documenting the investigator's assessment of each screened subject with regard to the protocol's inclusion and exclusion criteria has to be completed by the investigator.

Based on the results of Visit 1 assessments (see below 'Screening Assessments at Visit 1'), potentially eligible patients will enter a wash-out period as necessary. Blood test data generated by the study site or central laboratory 3 days prior to Visit 1 can be accepted.

Screening Assessments at Visit 1

- Demographics, medical history, including previous and concomitant diseases and treatments
- Physical examination
- Anthropometric measures (Height, Weight, Waist circumference, BMI)
- Vital signs (pulse rate, body temperature, respiratory rate, and blood pressure)
- Urine Pregnancy Test
- Blood samples for
 - lipid profile (total cholesterol, TG, HDL-C, LDL-C and LDL/HDL ratio)
 - biochemistry (serum creatinine for estimating GFR)

Patients will be instructed to come in fasted state for all subsequent study visits. Patients should receive information on a heart healthy diet and counseling on lifestyle changes as appropriate.

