9.4. Analysis Plan

General data analysis

For continuous endpoints, descriptive statistics including number, mean, median, standard deviation, minimum, maximum, and 95% confidence intervals will be presented. Continuous variables will be analyzed by means of ANOVA with Bonferroni adjustment. Paired T-Test will be used to compare the change from baseline within treatment groups. If the data strongly indicate a violation of the normal assumption, the non-parametric method of Kruskall Wallis test or Wilcoxon Signed-Rank Test will be applied for analysis.

For categorical endpoints, the count and percentages will be used to summarize the categorical data. The Chi-square test will be performed to test the difference between groups while Fisher's exact test will be applied for any counting of the frequency is less than 5.

All statistical analyses will be conducted using SAS software.

Endpoints

The primary efficacy endpoint for assessing the superiority of Antroquinonol to placebo will be analyzed using analysis of covariance (ANCOVA) model and baseline measurement as covariates, if the differences in baseline characteristics, such as gender, age, weight etc., are observed, for comparing the effectiveness between the treatment groups.

Analysis of other secondary efficacy endpoints (TC, HDL-C, LDL-C, and LDL/HDL ratio as well as the effect of Antroquinonol on E/E', baPWV and ABI and HU parameters) will be similar to the primary analysis of the primary endpoint. All tests will be based on a significance level of 0.05, without adjustment for multiple endpoints.

For the safety assessments, the information of adverse events will be described in detail. Count

and percentage will be tabulated for the number of patients with AEs, number of total AEs, number of patients with AEs associated to study dosing and intensity. Adverse events will be coded by the Medical Dictionary for Regulatory Activities (MedDRA®) adverse event dictionary. All the AEs will be categorized by each represented Preferred Terms (PT) and System Organ Class (SOC), which will be tabulated by body system with related incidence rates. The clinical laboratory tests and electrocardiogram tests will be analyzed to separate subjects into normal and abnormal categories, with number of subjects and percentage of subjects in each category, and McNemar's test or Fisher's exact test will then be applied to test the changes between each visit.

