### **9.2 Test of Assumptions**

The continuous variables will be compared using Student's t test (2 groups) or analysis of variance ( $> 2$  groups). If the conditions for applying these tests are not met normality assumption, the Wilcoxon rank sum (2 groups) or Kruskal-Wallis ( $> 2$  groups) non-parametric tests will be used. Comparison within group will be tested by using paired t test. If the normal assumption is violated, the Wilcoxon signed-rank test will be conducted. The category variables will be compared between groups using the Chi-square test if the theoretical total of each class studied is greater than 5. Otherwise Fisher's exact test will be used.

Protocol: GHLIP-2-001

Study Sponsor: Golden Biotechnology Corporation

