## 9.5 Safety Analyses

For the safety assessments, the information of adverse events will be described in detail. Count and percentage will be tabulated for the number of patients with AEs, number of total AEs, number of patients with AEs associated to study dosing and intensity. Adverse events will be coded by the Medical Dictionary for Regulatory Activities (MedDRA®) adverse event dictionary. All the AEs will be categorized by each represented Preferred Terms (PT) and System Organ Class (SOC), which will be tabulated by body system with related incidence rates. The clinical laboratory tests and electrocardiogram tests will be analyzed to separate subjects into normal and abnormal categories, with number of subjects and percentage of subjects in each category, and McNemar's test or Fisher's exact test will then be applied to test the changes between each visit.

Protocol: GHLIP-2-001

Study Sponsor: Golden Biotechnology Corporation

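### The only test assigned specifically to normal/abnormal laboratory and ECG results looks at change between visits, which does not answer the stated safety comparison with placebo

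*SAP*

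**What the plan says.** Protocol 2.2(4) makes the safety objective comparative: "To evaluate the safety and tolerability of 12 weeks of oral administration of Antroquinonol compared with placebo".

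For laboratory and ECG results split into normal and abnormal, SAP 9.5 states that "McNemar's test or Fisher's exact test will then be applied to test the changes between each visit". Protocol 9.4 uses the same sentence. Neither says whether the test is run per arm or over all arms together, or when McNemar's test applies and when Fisher's.

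Other parts of the plan bear on the same data:

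- **Descriptive.** The Protocol Summary (Statistical Methodology) says that "AEs, laboratory parameters, and vital signs will be reported descriptively".
- **Between groups, general.** SAP 9.2 says that "The category variables will be compared between groups using the Chi-square test", with Fisher's exact test otherwise. Protocol 9.4 (general data analysis) and the Protocol Summary have similar rules, plus ANOVA for continuous variables.
- **By-arm tables.** SAP 10.2 plans changes from baseline by treatment with 95% confidence intervals, counts below, within and above the normal range by treatment group, and shift tables. The SAP's planned tables list normal/abnormal and transition tables.
- **ECG.** SAP 10.3 compares the baseline ECG with later ones.
- **Adverse events.** SAP 10.1.1 has an explicit Fisher's test of System Organ Class rates across treatment groups. Laboratory and ECG shifts have no such explicit test.

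**The concern.** McNemar's test asks whether normal-to-abnormal and abnormal-to-normal moves are equally frequent. The safety objective asks whether the drug differs from placebo. The two questions part company when values drift for reasons unrelated to the study drug, and the protocol gives grounds to expect some drift. Patients on lipid-lowering drugs stop them for 14 days before treatment (Protocol 4.2, 7.2). Protocol 1.2 links such drugs to safety problems "such as the elevation of transaminase and rhabdomyolysis". At screening, "Patients should receive information on a heart healthy diet and counseling on lifestyle changes as appropriate".

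Two errors are possible. Drift common to all arms can produce a significant between-visit result in a dose arm with no drug effect. Conversely, new abnormalities on drug can be offset by abnormalities that resolve, so the test shows nothing. The randomised placebo arm removes shared drift, but the named test does not use it.

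**Working it through.** **Inputs from the documents.** 24 evaluable per arm and 20% dropout (Protocol 9.2); four arms, 1:1:1:1; two-sided 0.05 (SAP 7.12). Check of the arm size: 24/(1 − 0.20) = 30, and 30 × 4 = 120, as stated.

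**Assumed inputs.** The documents give no shift rates, so all rates below are illustrative.

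**Test.** Let b be the number who worsen and c the number who improve. The exact McNemar p-value is 2 × P[Bin(b + c, 0.5) ≤ min(b, c)], capped at 1.

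**Fixed examples, 30 per arm.**

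- Shared drift: 6 worsen and 0 improve on drug, and the same on placebo. McNemar in the drug arm: 2 × 0.5^6 = 0.031. Fisher's test, 6/30 against 6/30: p = 1.00.
- Cancelling: 8 worsen and 8 improve on drug. McNemar p = 1.00. New abnormalities of 8/30 against 1/30 on placebo: Fisher p = 0.026.
- Smallest detectable one-way shift: 5 against 0 gives 2 × 0.5^5 = 0.0625, so six are needed.

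**Rejection rate with no drug effect.** Sum the probabilities of all (b, c) with p < 0.05, where (b, c) is multinomial with the stated rates. Fisher's test compares the worsening rate on drug with the same rate on placebo.

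| Worsen / improve, every arm | McNemar per dose arm, n = 30 | n = 24 | Fisher v placebo, n = 30 |
|---|---|---|---|
| 5% / 2% | 0.2% | 0.1% | 0.2% |
| 10% / 5% | 2.2% | 1.1% | 0.9% |
| 10% / 2% | about 5% | 1.9% | 0.9% |
| 25% / 5% | 40% | 28% | 2.5% |
| 30% / 2% | 78% | 62% | 2.6% |

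At 25%/5% and n = 30, at least one of three dose arms is significant with probability 1 − (1 − 0.403)³ = 79%.

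**Masked harm, 30 per arm.** New abnormality is 35% on drug and 3% on placebo among patients normal at baseline; 60% of abnormal values resolve. With m patients normal at baseline, b ~ Bin(m, 0.35) and c ~ Bin(30 − m, 0.60) in the dose arm. Fisher's test compares m against m patients at 35% and 3%.

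| Normal at baseline | McNemar, dose arm | Fisher v placebo |
|---|---|---|
| 20 of 30 | 0.4% | 70% |
| 28 of 30 | 74% | 84% |
| 29 of 30 | 90% | 86% |

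The masking depends on how many patients start abnormal. With almost everyone normal at baseline, the two tests detect this harm about equally often.

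**Limit of any comparison here.** For 20% against 3% new abnormality at 30 per arm, Fisher's test has only 34% power. Zero events in 30 has an exact upper 95% limit of 1 − 0.025^(1/30) = 11.6%. Estimates with intervals will say more than p-values.

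**The case against.** The strongest reply is that the between-visit sentence is not the whole plan. SAP 9.2 compares categorical variables between groups and is not limited to efficacy. Protocol 9.4 applies its general rule to categorical endpoints, and laboratory and ECG changes are listed as safety endpoints. Fisher's test is also named in the disputed sentence and could be meant across arms. The by-arm summaries and shift tables let a reader set drug beside placebo, and abnormal laboratory findings can count as adverse events, whose System Organ Class rates are tested across groups.

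All of this stands. A reader might infer that laboratory safety is tested only within arms, or that the sponsor will treat shared drift as a drug effect. The documents support neither: per-arm testing is an inference, general between-group rules exist, and nothing says how a between-visit p-value will be interpreted. Nor do they show that a toxic dose would go unnoticed.

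The size is also open. Small drift gives rejection rates at or below 5%. Stopping drugs linked to raised enzymes, plus diet advice, may produce improvement, hence apparent benefit rather than false harm. Wash-out affects only prior users and precedes the Day 1 baseline, and its link to ECG, haematology or urinalysis is not shown.

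What remains is that the one rule written specifically for these data has a null without placebo, no text says which rule governs, and the safety sections promise no dose-minus-placebo estimate or interval.

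**Conclusion.** The point holds in this form: the only test the safety text assigns specifically to normal/abnormal laboratory and ECG results is of change between visits. McNemar's version does not address the comparison with placebo in Protocol 2.2(4). The sentence is also unreconciled with the general between-group rules and with the statement that laboratory data are descriptive.

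The consequence ranges from nothing to large. With no drug effect, rejection per dose arm runs from about 2% to 5% at 10% worsening to 78% at 30%/2%, while Fisher's test against placebo stays below 3%. Masked harm is a serious problem when a third of patients start abnormal (0.4% against 70%) and a minor one when 28 of 30 start normal (74% against 84%). These figures rest on assumed shift rates, 30 per arm, exact McNemar run per arm, and, for masking, 60% resolution. This is a cheap improvement, not a fault that invalidates the safety evaluation.

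**What to change.** In SAP 9.5 and Protocol 9.4, make the laboratory and ECG comparison dose versus placebo:

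- Among patients normal at baseline, report the proportion newly abnormal after baseline, at any visit and at Day 85, for each dose and placebo, with the risk difference and an exact or score 95% confidence interval.
- For continuous laboratory values, report the baseline-adjusted dose-minus-placebo difference in change with a 95% confidence interval.
- Keep the shift tables, and any between-visit tests, as description only. State that between-visit change will not be used to support or dismiss a drug effect.
- Say which rule governs these data, and align the Protocol Summary, the general paragraph of Protocol 9.4 and SAP 9.2 with it.

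A contrast of the pooled doses with placebo is optional.

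The cost is wording and a few more tables, with no new data. The intervals will be wide: 0 of 30 still allows up to 11.6%, and more where fewer than 30 patients are normal at baseline.

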## 9.6 Subgroup Analyses

The primary and secondary endpoints analyses will be performed by classified subgroup using ITT population and PP population. In addition, specified categorical or numeric characteristics if the demographic variables are statistically and clinically significant. The identified numeric variable will be classified by an appropriate cut-off point.

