## 8.3 Demographics

The following demographic and baseline characteristics will be ascertained at the time of study recruitment: gender, age, height, weight, BMI, pregnancy status (females only), medical history, physical examination, and concomitant medications. Continuous data will be summarized by descriptive statistics using number of specific item, mean, median, standard deviation,

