## 9.4 Secondary Endpoint Analyses

Analysis of other secondary efficacy endpoints (TC, HDL-C, LDL-C, and LDL/HDL ratio as well as the effect of Antroquinonol on E/E', baPWV and ABI and HU parameters) will be similar to the primary analysis of the primary endpoint by using ANCOVA model using baseline measurement as covariates, or using Kruskal-Wallis test when normal assumption is violated. Pairwise comparison will use two independent t-test or Wilcoxon rank-sum test, and performed significance level of 0.05 while statistical significance of ANCOVA or Kruskal-Wallis test treatment effect is achieved (Antroquinonol 50 mg vs. Placebo, Antroquinonol 100 mg vs. Placebo, Antroquinonol 150 mg vs. Placebo, Antroquinonol 100 mg vs. Antroquinonol 50 mg and Antroquinonol 150 mg vs. Antroquinonol 100 mg).

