## 9.7 Interpretation and Conclusion

All tests are two-tailed unless otherwise specified and the overall significant level is set to be 0.05. When the number of hypothesis in a test is increased, the Bonferroni correction would be used to test each of the individual tests at a significance level of  $0.05/m$  ( $m$ = number of tests=5, section 9.3). Statistical significance will be demonstrated if the p-value is less than the significance level of test. Regardless of the outcome declared statistically significant, all results could be stated on the Clinical Study Report (CSR).

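### SAP 9.6 ties subgroups to an undefined significance condition and an unstated cut-off, with no interaction test, error control or exploratory label, so its false-positive risk is uncontrolled

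*SAP*

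**What the plan says.** SAP 9.6 (Subgroup Analyses) has three sentences. The first sets the scope: "The primary and secondary endpoints analyses will be performed by classified subgroup using ITT population and PP population". The second is grammatically incomplete and gives the condition for adding subgroups: "specified categorical or numeric characteristics if the demographic variables are statistically and clinically significant". The third deals with numeric variables: "The identified numeric variable will be classified by an appropriate cut-off point".

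The related provisions are these:

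- SAP 9.7 sets the general level, "All tests are two-tailed unless otherwise specified and the overall significant level is set to be 0.05", and gives the Bonferroni divisor as "number of tests=5, section 9.3". Those five tests are the three dose-versus-placebo and two dose-versus-dose comparisons.
- SAP 9.4 lists the secondary endpoints as "TC, HDL-C, LDL-C, and LDL/HDL ratio as well as the effect of Antroquinonol on E/E', baPWV and ABI and HU parameters". Protocol 9.4 says of them: "All tests will be based on a significance level of 0.05, without adjustment for multiple endpoints".
- SAP 8.3 lists the characteristics recorded, beginning "gender, age, height, weight, BMI, pregnancy status (females only". Its only test of them is a comparison between arms at baseline.
- SAP 7.5 is headed as covering subgroups but names none. Protocol section 9 has no subgroup analysis, and the planned tables in the SAP appendix include none.
- Models 1 and 2 in SAP 9.3 contain main effects only.
- SAP 6.2 schedules a blinded data review before database lock and bars unblinding until the SAP is approved. Choosing subgroups or cut-offs is not listed as a task of that review.

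**The concern.** A subgroup analysis is interpretable when the variables and cut-offs are fixed without reference to treatment results, and when the question asked is whether the treatment effect differs between subgroups. SAP 9.6 secures neither.

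The variables enter through a test result, but the test is not identified. It could be imbalance between arms, association with outcome, or something else. The cut-off is left to later judgement. The analysis then tests for a treatment effect separately within each part. A significant result in one half and a non-significant one in the other does not show that the effect differs, yet no interaction test is planned to check this.

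At 24 evaluable or 30 enrolled patients per arm, a median split leaves about 12 to 15 per arm per half. SAP section 2 says planned analyses go into the regulatory submission and/or manuscripts, and nothing in 9.6 marks these as exploratory. What is at stake is the credibility of any subgroup claim. The primary and secondary conclusions do not depend on 9.6.

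**Working it through.** The documents give no error rate for the subgroup analyses, so there is no figure to reproduce. The check asks how often the procedure would show a subgroup effect on TG if the drug did nothing.

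**Inputs from the documents.** Four arms, 1:1:1:1; 24 evaluable and 30 enrolled per arm (Protocol 9.2); two-sided 0.05 (SAP 9.7); pairwise tests only after a significant omnibus test (SAP 9.3); nine endpoints, TG plus the eight in SAP 9.4.

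**Assumptions not in the documents.** Normal outcomes; candidate variables unrelated to outcome; cut-offs searched between the 20th or 25th and the 75th or 80th percentile; five candidate variables (gender, age, height, weight, BMI); correlation between endpoints 0 or 0.3; ITT only (adding PP would raise the rates slightly). Monte Carlo error is about 1 to 3 points.

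**Step 1: one variable, fixed split.** Two independent halves, each tested at 0.05, give 1 − 0.95² = 9.75%. Simulation gave 9.5% at 30 per arm and 10.8% at 24 per arm.

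**Step 2: one variable, free cut-off, 30 per arm, seven candidate cut-offs.**

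| Procedure | False TG subgroup effect |
|---|---|
| Omnibus test in each half, fixed median | 9.5% |
| Omnibus test in each half, any of seven cut-offs | 28% |
| Same, then a dose-versus-placebo t-test at 0.05 | 22% |
| Same, then Bonferroni at 0.05/5 = 0.01 | 12% |
| One interaction test, variable kept continuous | 5% |

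Repeat runs of the second row gave 26% to 28%. At 24 per arm with 13 candidate cut-offs the corresponding figure was 34.9%.

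**Step 3: does an interaction test alone solve it?** At 24 per arm, an interaction test at a cut-off fixed in advance had a false-positive rate of 5.1%. Taking the best of 13 cut-offs raised that to 25.4%. Both parts are needed: an interaction test, and no free choice of cut-off.

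**Step 4: apply the trigger strictly.** Read the condition as a baseline difference between arms at p < 0.05 in at least one of five variables, and run subgroups only then. At 24 per arm:

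- The trigger occurs in about 19% of trials.
- The overall chance of a false TG subgroup effect is 2-3% (fixed cut) or 5-6% (best of 11 cuts). At 30 per arm it is 2.8% or 7.2%.
- For any of nine endpoints the overall chance is about 13% or 17-18%.
- Given that the trigger has occurred (endpoint correlation 0), the TG rate is 0.025/0.194 = 13% or 0.053/0.194 = 27%.

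Reading significance as association with TG gives similar overall rates.

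**Step 5: no effective trigger.** If all five variables are examined, the TG rate is 29-30% (fixed cut) or 61-62% (best of 11 cuts). For any of nine endpoints it is 93-95% or about 100%.

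**The case against.** The strongest reply is that 9.6 is an incomplete paragraph and not a harmful rule. Several parts of that stand.

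- **Timing.** A reader might infer that the cut-off is chosen after outcomes have been seen. The text does not say so. An appropriate cut-off could be a conventional clinical threshold, and SAP 6.2 leaves room for a blinded choice. But nothing requires a blinded choice, so the point that stands is that timing is open.
- **The trigger.** It concerns demographic variables, and the text requires clinical as well as statistical significance. It does not select subgroups because the drug appeared to work in them, and applied strictly it keeps the overall TG rate low (step 4).
- **The omnibus gate.** Ungated dose-versus-placebo t-tests over seven cut-offs give about 53%. That figure should not be used, because SAP 9.3 allows pairwise tests only after a significant omnibus result. The gated rates are those in step 2.
- **Consequences.** No planned table reports a subgroup result, and the SAP does not say that within-subgroup significance will be read as a differential effect.

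What the reply does not remove is the written commitment to within-subgroup testing, with selection by significance, no interaction test and no error rule. Filling in a cut-off value alone would still leave about 9-10% per variable, and no test of whether the effect differs.

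**Conclusion.** The point holds as a lack of control. One might go further and conclude that a false subgroup finding is likely even with an inactive drug. The documents do not support that in general: it holds only if variables and cut-offs are searched freely, or if all endpoints are searched once a subgroup has been triggered.

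On TG, the chance of a false subgroup effect runs from about 2% (strict imbalance trigger, fixed cut) to about 62% (all five variables, free cut-offs). With one variable already under examination it is about 9-10% or 28%. Two analysts could both follow 9.6 and sit at opposite ends of that range. The figures rest on the assumed cut-off grids, five candidate variables and normal outcomes. The absence of an interaction test, a subgroup error rule and an exploratory label does not depend on those assumptions.

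This should be corrected, but it does not affect the primary result.

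**What to change.** Before unblinding, rewrite SAP 9.6 as follows:

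1. Delete selection by significance. Baseline imbalance is already dealt with by covariate adjustment (Model 2, SAP 9.3).
2. Name a short list of baseline variables already collected, for example sex, age, BMI and baseline TG.
3. Test each by one treatment-by-variable interaction added to the TG ANCOVA, with numeric variables kept continuous. Say that this model is used even if Kruskal-Wallis replaces the main test, since Kruskal-Wallis carries no interaction term.
4. Show within-subgroup estimates with confidence intervals for display only, at cut-offs fixed before unblinding, such as the blinded pooled median.
5. Label all subgroup results exploratory. Four interaction tests at 0.05, if independent, carry a chance of 1 − 0.95⁴ = 18.5% of at least one false positive. If any claim is intended, use 0.05/4 = 0.0125.

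The cost is SAP wording and a few model terms, with no new data.

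The drawback is power. With 24 per arm and the protocol's SD of 40, a dose-versus-placebo difference has standard error 40 × √(2/24) = 11.5. The difference between two halves of 12 per arm has 40 × √(4/12) = 23.1, twice as large. The effect detectable with 90% power therefore rises from 37.4 to about 74.9 percentage points. Keeping variables continuous avoids losing information to the split, but few subgroup claims will be possible.
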